9.2 General methodology

Data from repetitions of visual acuity tests, PERG, VEP, OCT will be expressed as the average difference between two recordings obtained during separate sessions + / - the standard deviation of this difference. The 95% confidence limits of the test-retest variability will be established by assuming a normal distribution of the data, after verification using the Anderson-Darling and Kolmogorov-Smirnov tests, calculating the average of the differences and the relative standard deviations.

For each group (NAION Control eyes and NAION eyes Treated with Cisticoline), differences in visual acuity values, PERG and VEP and OCT responses measured at 6 and 9 months from

baseline will be assessed using ANOVA and the $p < 0.05$ value will be considered significant. Multiple comparisons will be made using the Tukey and Games-Howell methods, establishing the value of the error rates at 5%.

Correlations between the electric-physiological measurements (PERG/VEP) and field of view measurements, normalized in logarithmic value, both at Baseline and at each follow-up time, for each group will be performed using Pearson's test and the $p < 0.05$ value will be considered significant.

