2. OBJECTIVES AND AIMS OF THE STUDY

2.1 Primary objective

Evaluation of potential neuroprotective action of Citicoline for maintenance and stabilisation of visual acuity in patients with Non-arteritic Ischemic Optic Neuropathy (NAION).

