5.3 Trial term and visits

The study will have a total duration of 9 months, during which period the patients will have 3 visits:

- baseline visit T0
- visit at 6 months T1
- visit at 9 months T2

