5.5 Outcomes

The visual function will be determined by [Visual] acuity assessment, the function of retinal ganglion cells RGC will be assessed by electroretinogram (PERG) and the optic nerve function will be evaluated using the Visual Evoked Potential (VEP).

The primary objective is to evaluate the stabilisation and/or improvement in visual acuity.

Secondary objectives include stabilising and/or improving RGC functionality and optic nerve function assessed with the recording of PERG and VEP. Correlations will also be evaluated between stabilisation and/or function improvement of RGC and the optic nerve with changes in the visual field and the morphology of the optic nerve head (evaluated by OCT).

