5.6 Efficiency parameters

- For the VA examination, the visual acuity values will be recorded for distance and near vision corrected with the best optical correction.
- For the visual field examination, the following parameters will be recorded: mean deviation (MD), pattern standard deviation (PSD), number of points, with $p < 5\%$ and $< 1\%$ in the pattern deviation map and the total deviation map.
- Each PERG examination will record the following parameters: latency P50 and amplitude P50-N95.

- The following parameters will be recorded for each VEP test: latency N75 and P100, amplitude N75-P100 and P100-N145
- For each OCT imaging session the following parameters will be recorded: the average thickness of the retinal nerve fibre layer and the thickness divided according to sectors.
- At baseline and at each control visit (6 and 9 months) a complete eye examination will be performed including the following assessments: corrected visual acuity, biomicroscopy, indirect ophthalmoscopy, measurement of intraocular pressure with Goldmann applanation tonometer, field of vision testing, recording of PERG and VEP, imaging of the optic nerve and retinal nerve fibre layer with OCT.

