10. EXPECTED RESULTS AND NEUROFUNCTIONAL CONSIDERATIONS

10.1 Expected results and their impact in clinical practice

Reducing the loss of visual acuity achieved through stabilization or improvement of optic nerve and retinal function could ultimately lead to a reduction in visual disability secondary to non-arteritic ischaemic neuropathy, with a significant reduction in related costs for the National Health Service.

In NAION patients treated with Citicoline oral solution, one of the following conditions may be observed at the end of follow-up:

- 1) further loss of retinal nerve fibres (OCT with reduced RNFL thickness) and functional reduction of RGCs (PERG reduced in amplitude) and of the Optic nerve (increase in implicit time P100 of VEP);
- 2) further loss of retinal nerve fibres (OCT with reduced RNFL thickness) and functional maintenance of RGC (PERG with unchanged amplitude) and Optic nerve (implicit time P100 of the VEP unchanged);
- 3) maintenance of retinal nerve fibres (OCT with unchanged RNFL thickness) and functional maintenance of RGC (PERG with unchanged amplitude) and Optic nerve (implicit time P100 of the VEP unchanged);
- 4) maintenance of retinal nerve fibres (OCT with unchanged RNFL thickness) and functional increase of RGC (PERG with increased amplitude) and optic nerve (implicit time P100 of VEP reduced);
- 5) improvement of retinal nerve fibres (OCT with increased RNFL thickness) and functional increase of RGC (PERG with increased amplitude) and Optic nerve (implicit time P100 of

VEP reduced);

The results of NAION patients treated with Cisticoline for oral suspension will be compared with those of NAION patients given no treatment to assess the natural evolution of the morpho-functional condition. The following conditions may occur in such patients:

- 1) further loss of retinal nerve fibres (OCT with reduced RNFL thickness) and functional reduction of RGCs (PERG reduced in amplitude) and of the Optic nerve (increase in implicit time P100 of VEP);
- 2) further loss of retinal nerve fibres (OCT with reduced RNFL thickness) and functional maintenance of RGC (PERG with unchanged amplitude) and Optic nerve (implicit time P100 of the VEP unchanged);
- 3) maintenance of retinal nerve fibres (OCT with unchanged RNFL thickness) and functional maintenance of RGC (PERG with unchanged amplitude) and Optic nerve (implicit time P100 of the VEP unchanged);

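### The planned within-group test of change in acuity at p<0.05 cannot show stabilisation, so that half of the primary objective is left to rest on a non-significant result

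*Combined protocol and SAP*

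**What the plan says.** Section 2.1 sets the primary objective as "Evaluation of potential neuroprotective action of Citicoline for maintenance and stabilisation of visual acuity". Section 5.5 widens it: "The primary objective is to evaluate the stabilisation and/or improvement in visual acuity". Section 9.1 uses the wider form and sizes the trial on a pilot improvement of 0.35 LogMAR from baseline.

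For acuity, section 5.6 says only that "the visual acuity values will be recorded for distance and near vision corrected with the best optical correction". It gives no threshold of change.

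Section 9.2 gives two procedures that touch acuity:

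- Repeat tests are summarised as "the average difference between two recordings obtained during separate sessions", with the SD of that difference. From these, "The 95% confidence limits of the test-retest variability will be established by assuming a normal distribution of the data". No use is assigned to the limits.
- Within each group, differences from baseline at 6 and 9 months are assessed by ANOVA at p<0.05, with Tukey and Games-Howell multiple comparisons.

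On timing, section 5.3 states: "The study will have a total duration of 9 months, during which period the patients will have 3 visits". Sections 5.2 and 5.4 place these at baseline, 6 and 9 months and show no retest session.

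**The concern.** A test of no change answers whether the data contradict zero change. If they do not, the result is compatible with stability, but also with any loss too small for that sample to detect. Section 9.2 states no equivalence or non-inferiority margin and no rule for a stable or worsened eye. It also plans no confidence interval for the change and no between-arm comparison of acuity. The improvement half of the objective can be tested as planned. The stabilisation half has no criterion of its own and is left to rest on p>0.05.

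This also creates a poor incentive: the fewer the eyes and the noisier the measurements, the easier it is to report no significant change.

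The test-retest limits could help to separate noise from change, but they need two sessions between which nothing real has happened. The scheduled visits are at least three months apart and span treatment or its suspension. Any pair drawn from them mixes true change into the noise.

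**Working it through.** **1. The plan's own figure.** Section 9.1 gives acuity SDs of 0.122 (baseline) and 0.107 (60 days) and treats them as independent samples.

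- Common SD = √[(0.122² + 0.107²)/2] = 0.1147; standardised difference = 0.35/0.1147 = 3.05.
- A two-sided 5% two-sample t-test with 90% power needs 4 eyes per group. The plan states 5, where power is 98.7%.
- The PERG figure of 12 reproduces exactly, and 12 × 1.3 = 15.6 gives the planned 16.

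The arithmetic is not at fault. It answers whether a large improvement can be detected, not whether a loss can be excluded.

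**2. SD of within-eye change.** SD_change = √(0.122² + 0.107² − 2r × 0.122 × 0.107). The documents give no within-eye correlation r, so 0, 0.5 and 0.8 are assumed.

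**3. Largest observed mean loss that stays non-significant.** A paired t-test approximates the planned ANOVA: limit = t(0.975, n−1) × SD_change/√n, with t = 2.131 for n = 16.

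**4. Chance that a true loss is non-significant.** From the noncentral t with noncentrality = loss × √n/SD_change.

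| | r = 0 | r = 0.5 | r = 0.8 |
|---|---|---|---|
| SD of change (LogMAR) | 0.162 | 0.115 | 0.074 |
| Largest non-significant observed mean loss, n = 16 | 0.086 | 0.061 | 0.039 |
| True loss 0.05, n = 16: non-significant | 79% | 63% | 28% |
| True loss 0.10, n = 16: non-significant | 36.5% | 10% | 0.1% |
| True loss 0.05, n = 12: non-significant | 84% | 72% | 43% |
| True loss 0.10, n = 12: non-significant | 51% | 22% | 1% |

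If the ANOVA treated the three visits as independent samples with Tukey comparisons, an observed mean change would have to exceed about 0.098 LogMAR (n = 16) or 0.115 (n = 12) to be significant.

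**5. What 16 eyes per arm can exclude.** Half-width of the 95% CI for the between-arm difference in change = t(0.975, 30) × SD_change × √(2/16) = 2.042 × SD_change × 0.3536. This gives 0.117, 0.083 and 0.053 LogMAR for r = 0, 0.5 and 0.8, treating eyes as independent.

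As a non-inferiority question (SD of change 0.115, one-sided 2.5%, 90% power, true difference zero), the eyes needed per arm are 111 for a margin of 0.05, 28 for 0.10, 13 for 0.15 and 7 for 0.20. The planned 16 cover 0.15 but not 0.10.

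**6. Why a per-eye test-retest limit is the wrong margin for a mean.** Suppose, for illustration, that the test-retest SD equalled 0.115. The per-eye limit would be 1.96 × 0.115 = 0.226 LogMAR. With a within-arm CI half-width of 0.061, an observed mean loss up to about 0.164 LogMAR would pass as stable. The p>0.05 reading stops at 0.061, so this rule would be looser.

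**The case against.** The plan nowhere says that p>0.05 means stabilised. A reader might infer that a non-significant change will be reported that way, but the text supports only that it offers no other criterion for acuity.

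Stabilisation could also mean less loss than in untreated eyes. Section 10.1 does say that treated results will be compared with those of untreated patients, and the third secondary objective compares arms on OCT. That shows intent, but section 9.2 turns it into no between-arm test or interval for acuity.

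A reader might also take the lists in 10.1 as a classification that denies control eyes an improved state, since entries such as "maintenance of retinal nerve fibres (OCT with unchanged RNFL thickness) and functional maintenance of RGC (PERG with unchanged amplitude" have no cut-off and the improved entries appear only for treated patients. The documents do not support this. The lists describe results that may be seen on OCT, PERG and VEP, they do not cover acuity, and nothing says eyes will be counted into them. They form no part of this point.

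On size, the exposure is mainly to small losses: at r = 0.5, a true loss of 0.10 LogMAR is missed only 10% of the time with 16 eyes. That stands.

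On retests, section 9.2 does plan repeat sessions and does not tie them to the three visits. It would be too strong to say that the limits will be computed from follow-up pairs. What stands is that no retest session is scheduled. Section 5.4 mentions screening before baseline, but the table in 5.2 gives it no column and section 6 describes one combined baseline screening visit. A separate pre-treatment acuity cannot be assumed.

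**Conclusion.** The point holds for the stabilisation half of the primary objective. The stated test cannot support that claim, no margin is given, and the schedule shows no session from which clean test-retest limits could be obtained. With 16 eyes, a true mean loss of 0.05 LogMAR would be non-significant 28% to 79% of the time, and one of 0.10 between 0.1% and 36.5%.

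These figures rest on the pilot SDs in 9.1, an assumed within-eye correlation of 0.8 to 0, a paired t-test in place of the planned ANOVA, and independent eyes. Sections 4 and 5.1 allow both eyes of a patient to enter; positive correlation between fellow eyes would lower the effective sample size. The material between sections 2.2 and 4 was not available, so a definition of stability there cannot be excluded.

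**What to change.** Amend section 9.2 before the key is opened:

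- **(a) Estimates.** Report the mean LogMAR change in each arm and the between-arm difference in change at 6 and 9 months, with 95% CIs. Make these the basis for any stabilisation claim.
- **(b) Criterion.** State that p>0.05 for change from baseline is not evidence of stabilisation. Require the CI to exclude a loss larger than a group-mean margin that is justified and fixed before unmasking. Do not use the per-eye test-retest limit as that margin.
- **(c) Test-retest limits.** State that they will not be calculated from T0–T1, T0–T2 or T1–T2 pairs. If pre-treatment repeats exist, use the limits only for a supportive per-eye description, with the same improved, stable and worsened states in both arms.

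Parts (a) and (b) need only wording and a table from acuity data already scheduled. Part (c) costs nothing if no repeats exist; adding new repeat sessions would mean extra procedures and a protocol amendment under section 15.1. The real cost is that stabilisation becomes harder to claim. With a between-arm half-width of about 0.05 to 0.12 LogMAR, 16 eyes per arm can exclude only a fairly wide margin, and the report should say so.

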2.2 Secondary objectives

- 1) to study the neurodegenerative processes of the optic nerve in patients suffering from NAION using the correlations between the function of RGC and optic nerve (using the PERG and VEP recording) and the structural modifications of the nerve fibres of the optic nerve (using the OCT evaluation);
- 2) to determine in patients with NAION the potential for neuroenhancement linked to Citicoline administration in oral solution. This will be obtained using the evaluations of the functional condition (PERG/VEP) found after treatment with Citicoline compared to the condition at the time of enrolment. Correlations will also be evaluated between stabilisation and/or function improvement of RGC and the optic nerve with changes in the visual field.
- 3) to study in patients with NAION the potential for neuroprotection linked to Citicoline administration oral solution. This will be evaluated by comparing, at the end of a 9-month follow-up period, the changes of the nerve fibre structure and the optic nerve (via the OCT assessment) found in the group of patients with NAION treated with Citicoline oral solution compared to a group of patients with untreated NAION where the natural progression of neurodegenerative processes will be observed.

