5. TRIAL DESIGN

5.1 Trial Plan

A prospective, single-center, randomized, blinded close-label study providing for the enrolment of a minimum of 16 to a maximum of 32 patients (see sample size in the section "Statistics") affected by NAION.

Considering that according to the inclusion/exclusion criteria it is very difficult to recruit patients suffering from NAION with the specific characteristics that enable them to be enrolled in this study, it is likely that with the presence of the binocular NAION, both eyes of the patients will be considered as recruited. Therefore, in the event of all patients having monocular NAION, enrolment must include 32 patients and this number is lower if we need to enrol patients with NAION in both eyes.

Patients selected according to the inclusion/exclusion criteria after signing informed consent will be randomized into two groups:

- a) In one group of patients with NAION no type of treatment will be performed (16 eyes, Control Group)
- b) in another group of patients with NAION, Citicoline will be administered in oral solution (500 mg/day) for 6 months followed by three months of suspension (16 eyes, Treated Group)

The division into two groups will enable the identification of a specific neuroprotective action of Citicoline. Randomization will be done by dividing patients with similar characteristics including age, refraction and visual impairment (perimeter defect and visual acuity) into two groups. Patients will be assigned to each group by an investigator not involved in the functional and structural tests.

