6. ASSIGNMENT AND MASKING

Patients will be selected from a large cohort of known NAION patients who have been attending our facility for at least 12 months (approximately 125 patients). Only patients who meet the inclusion criteria will be selected. Patients will perform a baseline screening visit during which the conditions corresponding to the inclusion criteria will be evaluated and the study proposed. Only after signing the informed consent, will a single investigator ("recruiting doctor"), not involved in the clinical and instrumental assessments, decide whether to assign the selected patient to the Citicoline-treated or non-Citicoline-treated group.

The assignment to either group will take place in sequential order of presentation of the patient (with a 1:1 probability of being assigned to one or the other group) in order to constitute two homogeneous groups in terms of number.

The aforementioned assignment will be known only to the patient and the "recruiting doctor" who will not be involved in the clinical and instrumental assessments envisaged by the research and will therefore be the only investigating doctor to know the group to which the selected patient belongs; this feature of the study will be used to ensure "objectivity" of the clinical and instrumental assessments and to prevent them from being influenced in any way by the knowledge that the patient examined has or has not been treated with Citicoline. In this regard, it should be noted that the patient, by signing the informed consent, promises not to provide any type of information regarding the group to which he/she belongs and/or any treatment administered to other staff of the Institute involved in the clinical and instrumental assessments apart from the "recruiting doctor".

As a result, throughout the duration of the study (both at baseline and at the 6 and 9 month visits),

all study assessments (AV, CV, VEP, PERG, OCT) will be conducted by investigators who do not know if the patient being examined belongs to the Citicoline-treated or non-Citicoline-treated group.

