Based on known preliminary data (Parisi et al, 2008), considering the implicit time P100 of the VEP and a power value = 90% ($\alpha = 5\%$) it is deemed reasonable to include in the study $N = 11$ observations (eyes tested) per group. The sample number has been calculated based on the difference in the implicit time P100 of the VEP measured after 60 days of treatment with Cisticoline for oral suspension compared to the baseline of 15 ms (Baseline P100: mean 141 ms, a standard deviation; P100 at 60 days: mean 126 ms, a standard deviation: 9.8 ms).

To summarise, the size from the sample estimated on the basis of the primary objective (visual acuity) is $N= 5$; the size from the sample estimated on the basis of secondary objectives (PERG and VEP) is $N=12$ and $N=11$, respectively.

Considering the larger sample size ($N=12$, PERG), and assuming the presence of outliers and the potential voluntary withdrawal from the study by patients, the sample is increased by 30%, so it is considered appropriate to reach $N=16$ observations (eyes tested) per group (NAION Treated with Cisticoline and NAION not treated).

In this calculation of the sample, it is not possible to estimate a priori the sample number relative to the secondary objective – point 3 (see Point 2.2), as data in the literature are not currently available regarding possible changes in the structure of nerve fibres and the optic nerve (assessed by OCT) following treatment with Cisticoline.

The calculation procedure was carried out using the Minitab v.12.7 and Gpower 3.1 programmes, assuming that the averages and standard deviations of all the parameters considered come from two independent samples: Patients with NAION in baseline condition and patients with NAION after 60 days of treatment with Cisticoline in oral suspension (Parisi et al, 2008).

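### The specified efficacy tests compare each arm with its own baseline; no treated-versus-control test and no primary visit is set for visual acuity, the primary outcome

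*Combined protocol and SAP*

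**What the plan says.** Section 9.2 gives the efficacy analysis in one sentence. "For each group (NAION Control eyes and NAION eyes Treated with Cisticoline), differences in visual acuity values, PERG and VEP and OCT responses" are assessed by ANOVA at months 6 and 9 against baseline, with p<0.05 as the criterion. Tukey and Games-Howell comparisons follow at a 5% error rate, without naming the pairs. The correlations are also per group.

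The outcome section states that "The primary objective is to evaluate the stabilisation and/or improvement in visual acuity". It gives neither a comparator nor a visit.

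A comparison of arms is intended elsewhere:
- Section 5.1: "The division into two groups will enable the identification of a specific neuroprotective action of Citicoline".
- Section 2.2, objective 3, compares nerve-fibre changes at 9 months "found in the group of patients with NAION treated with Citicoline oral solution compared to a group of patients with untreated NAION". This concerns OCT only.
- Section 10.1: "The results of NAION patients treated with Cisticoline for oral suspension will be compared with those of NAION patients given no treatment". The outcomes it lists are OCT, PERG and VEP.

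Section 5.4 sets when the key is opened (after 9 months) but does not make that the primary visit. Section 9.1 bases the sample size on two samples: "Patients with NAION in baseline condition and patients with NAION after 60 days of treatment with Cisticoline in oral suspension". The control arm is neither of them.

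**The concern.** The control arm exists so that change under citicoline can be set against change without it. Separate tests against baseline do not do that. Any change common to both arms (natural course, learning of the test, regression to the mean) enters the treated arm's p-value and can be read as a drug effect. One arm crossing 0.05 while the other does not is a comparison of two p-values, not an estimate of the difference between arms.

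Leaving the visit open adds a second choice. Treatment stops at month 6 and month 9 follows three months without it, so the two visits answer different questions. As written, both the contrast and the visit could be chosen after the key is opened.

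**Working it through.** **1. The plan's own sample size (section 9.1).** Pooled SD = √((s₁² + s₂²)/2), two-sample t-test, two-sided 5%, 90% power.
- Acuity: change 0.35 LogMAR, SDs 0.122 and 0.107. Pooled SD 0.115, d = 0.35/0.115 = 3.05. Four eyes per group give 94.5% power; the stated 5 give 98.7%.
- PERG: change 0.38 microvolts, SDs 0.29 and 0.25. Pooled SD 0.271, d = 1.40. Twelve eyes give 90.7%, matching the stated 12.
- VEP: change 15 ms, one SD of 9.8 ms given. If the baseline SD is assumed equal, 11 results, as stated.
- Allowance: 12 × 1.3 = 15.6, so 16.

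The arithmetic is sound within one eye. The effect sizes, however, are before-after changes in treated patients.

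**2. Within-arm testing of an inert product.** 16 independent eyes per arm, one visit, a t-test of change in each arm, the same true drift in both. Let p be the probability that an arm is significantly improved (noncentral t, 15 df, noncentrality = drift/SD × √16). Treated improved and control not: p(1 − p).

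| Assumed drift (SD of change) | Treated arm improved | Treated improved, control not |
|---|---|---|
| 0 | 2.5% | 2.4% |
| 0.25 | 15.3% | 13.0% |
| 0.5 | 46.5–46.8% | 25% |

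A two-sided between-arm test rejects in about 5% at every drift, and in the treated arm's favour in 2.5%. The latter is the like-for-like comparator.

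**3. The same in LogMAR.** SD of change = √(0.122² + 0.107² − 2r × 0.122 × 0.107), which is 0.162, 0.115 and 0.074 for an assumed baseline-to-follow-up correlation r of 0, 0.5 and 0.8.

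| Assumed common improvement | Treated arm improved (r = 0 / 0.5 / 0.8) | Treated improved, control not |
|---|---|---|
| 0 | 2.5% throughout | 2.4% throughout |
| 0.02 | 6.7 / 9.5 / 17.3% | 6.3 / 8.6 / 14.3% |
| 0.05 | 21.0 / 36.9 / 71.7% | 16.6 / 23.3 / 20.3% |

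**4. What a between-arm test must allow for.** Section 5.1 says that in binocular disease "both eyes of the patients will be considered as recruited". In simulation with 16 eyes per arm and an assumed inter-eye correlation of 0.3, 0.5 or 0.8, a t-test that treats eyes as independent has a type I error of about 9%, 11% or 16% if all patients are bilateral (8 per arm), and 7%, 8% or 10% if half the eyes come from bilateral patients. With all patients bilateral, a test on patient means stays at about 5%. Cluster-robust errors with 16 patients give 7.3–7.5% with a normal reference and 5.2–5.4% with t on 14 df.

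**5. What the planned N can detect between arms.** Difference at 90% power = k × 0.107 × √(1 − r²), where k is the standardised detectable difference for the two-sample t-test. The degree of freedom for the covariate is ignored.
- 16 eyes per arm, k = 1.185: 0.127, 0.110 and 0.076 for r = 0, 0.5 and 0.8.
- 12 eyes per arm, if the whole 30% allowance is used up, k = 1.385: 0.148 to 0.089.
- All bilateral, 8 patients per arm, k = 1.745, times √((1 + ρ)/2) for inter-eye correlation ρ of 0.3 to 0.8: 0.090 to 0.177.

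**The case against.** The strongest reply is that section 9.2 leaves the ANOVA factors and the post-hoc pairs undefined. Games-Howell is a procedure for independent groups with unequal variances, so it fits an arm contrast better than repeated visits of the same eyes. The same sentence covers OCT, for which objective 3 requires a comparison of arms, and a strictly within-arm reading leaves that objective without a test. A between-arm comparison may therefore have been meant. That is a fair reading of intent, but the sentence is scoped to each group, its differences are from baseline, and no group factor or arm pair is named.

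The 9-month unmasking and the 9-month OCT comparison point towards month 9 without setting it for acuity.

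The error rates do depend on the form of ANOVA. Counting treated improved at either follow-up visit and control not, at a drift of 0.25 and 0.5 SD, repeated-measures ANOVA with Tukey gives about 12% and 25%, close to the figures above. One-way ANOVA that treats visits as independent gives about 2 to 3% and 13 to 14% at r = 0.5, and 1% or less at r = 0.8. Drift may also be small: section 1.1 reports slight spontaneous improvement only in rare cases, and entry requires an episode more than 6 months old. These points make the percentages illustrative; they do not supply the missing test.

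On sample size, treating baseline as a stand-in for an unchanged control group is possible. Section 9.1 is open about its source, so the gap there is a missing between-arm difference, not a concealed one.

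**Conclusion.** The concern holds, and it must be fixed before analysis. The only efficacy test specified cannot support the conclusion that section 5.1 draws from having two groups, and neither the arm contrast nor the visit for the primary outcome is fixed. This does not depend on drift: at zero drift the false-positive rate is not raised, yet the treatment effect is still not estimated by any specified test. If both arms share a drift of 0.25 to 0.5 SD, within-arm testing by t-test or repeated-measures ANOVA would single out an inert treatment in roughly 12 to 25% of trials, against 2.5% for a valid comparison. The drift and the correlations are assumptions; the SDs are those of section 9.1.

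**What to change.** - **Primary analysis:** one treated-versus-control comparison of best-corrected distance acuity in LogMAR, the scale of section 9.1, adjusted for baseline acuity, with the difference and its 95% CI.
- **Visit:** month 6 or month 9, chosen by the sponsor before unmasking, with a statement of which question it answers.
- **Two eyes:** a patient random effect, cluster-robust errors or a patient-mean analysis, with degrees of freedom based on the number of patients.
- **Other outcomes:** the same between-arm model for PERG, VEP and OCT as secondary outcomes; within-arm changes descriptive only.
- **Section 9.1:** keep the stated source of N and add the between-arm difference that it can detect.

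The cost is an amendment submitted to the Ethics Committee (section 15.1) and a re-justified N, with no new measurements. All the detectable differences shown lie below the 0.35 LogMAR change used for sizing, so more patients are needed only if the expected difference between arms is smaller than those figures or the SD is larger.

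The change does not remove expectation effects. Section 6 says of the allocation: "The aforementioned assignment will be known only to the patient" and the recruiting doctor. An assumed expectation difference of 0.25 or 0.5 SD would make the between-arm test significant in about 11% or 28% of trials of an inert product. The report should state this limit.

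### Section 9.2 tests acuity, PERG, VEP and OCT parameters alike at 5% with no order or adjustment across them: roughly a 20–49% chance of at least one false positive for 9–13 parameters

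*Combined protocol and SAP*

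**What the plan says.** The testing rules are in section 9.2. The analysis is by arm: "For each group (NAION Control eyes and NAION eyes Treated with Cisticoline), differences in visual acuity values, PERG and VEP and OCT responses" at 6 and 9 months are compared with baseline, and the changes from "baseline will be assessed using ANOVA and the $p < 0.05$ value will be considered significant". The adjustment that follows is "Multiple comparisons will be made using the Tukey and Games-Howell methods, establishing the value of the error rates at 5" per cent. Visual field is not in the ANOVA list; it enters through "Correlations between the electric-physiological measurements (PERG/VEP) and field of view measurements", tested by Pearson's method at p<0.05 for each group and each visit.

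Section 5.6 sets out what is recorded in each domain. For acuity, "the visual acuity values will be recorded for distance and near vision". PERG has one latency and one amplitude; VEP has two latencies and two amplitudes. OCT gives "the average thickness of the retinal nerve fibre layer and the thickness divided according to sectors", with no number of sectors. For the visual field it lists "mean deviation (MD), pattern standard deviation (PSD), number of points" below two probability cut-offs.

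Sections 2.1 and 5.5 make visual acuity the primary objective, and 2.2 and 5.5 make the other domains secondary. Section 9.1 sizes the study on acuity (5 eyes per group), PERG P50-N95 amplitude (12) and VEP P100 (11), each at 90% power and a full 5%. The final 16 per group comes from the PERG figure. Section 10.1 describes the possible results as patterns of nerve fibre layer thickness, PERG amplitude and VEP P100.

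**The concern.** Tukey and Games-Howell compare the levels of a factor (here, the visits) for one outcome. A reader may take the 5% in that sentence as control for the whole study, but nothing in 9.2 links one parameter's test to another's. There is no order, no division of alpha and no condition that acuity succeed first. The priority given to acuity in 2.1 and 5.5, and the narrower choice of PERG amplitude and VEP P100 in 9.1, are not carried into the analysis.

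At stake is how a mixed result is read. If acuity shows nothing and one VEP amplitude or one nerve fibre layer sector falls below 0.05, the plan as written calls that result significant and gives no pre-stated basis for discounting it. The primary outcome has a similar gap: distance or near acuity, at 6 or 9 months, within the treated group or against control, could each be presented as the deciding result.

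**Working it through.** **The plan's own figures.** The documents state no error rate across outcomes, so there is none to reproduce. The sample size shows how alpha is used. For PERG, the pooled SD is √((0.29² + 0.25²)/2) = 0.271, so d = 0.38/0.271 = 1.40. A two-sided two-sample t-test at 5% then needs 12 per group (power 90.7%), matching 9.1; a one-sided test would need 10. So 9.1 fits a two-sided 5% spent in full on one outcome.

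**Number of parameters.** From 5.6, limited to the domains in the 9.2 ANOVA: 2 acuity + 2 PERG + 4 VEP + 1 mean nerve fibre layer thickness = 9. The number of sectors is not given. I assume four at the upper end, which makes 13.

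**Correlation between parameters.** Not in the documents. I take a common correlation r from 0 to 0.7 as an assumption.

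**Chance of at least one false positive, one two-sided 5% test per parameter, no true effect.**
- Independent: 1 − 0.95^k.
- Correlated: k equicorrelated standard normal statistics, counting any with |z| > 1.96 (simulation and numerical integration agree to within about 0.2 percentage points).

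| Parameters (k) | r = 0 | r = 0.5 | r = 0.7 |
|---|---|---|---|
| 4 (one per domain) | 18.5% | 15.6% | 13.0% |
| 9 (countable) | 37.0% | 26.9% | 20.2% |
| 13 (four sectors assumed) | 48.7% | 33% | 24.1% |

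**Beneficial direction only.** Each test has 2.5% in that tail. For 13 independent parameters, 1 − 0.975^13 = 28.0%; for 9, 1 − 0.975^9 = 20.4%. Counting only z > 1.96 in the correlated model gives 10.1% for 9 parameters and 12.0% for 13 at r = 0.7. The range is about 10–28%.

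**Each group tested separately, as 9.2 plans.** With different patients in the two arms, the chance is 1 − (1 − p)². For 13 parameters: 1 − (1 − 0.487)² = 74% at r = 0, and 1 − (1 − 0.241)² = 42% at r = 0.7. For 9 parameters: 1 − (1 − 0.370)² = 60% and 1 − (1 − 0.202)² = 36%. The Pearson tests are not counted in any of these figures.

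**The case against.** The strongest reply is that acuity is named primary, has its own sample size calculation, and everything else is labelled secondary. In a 32-eye single-centre study, secondary outcomes may need only cautious reporting. Section 10.1 also narrows interpretation to three measures read as joint patterns. Much of this stands: a single pre-set acuity test would not be inflated by the secondary tests. But 9.2 sets no such single test, its significance rule covers the secondary outcomes equally, and the patterns in 10.1 do not include acuity and are not a testing rule.

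A reader might infer several stronger things that the documents do not support.

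- That every recorded parameter is tested. Visual field indices are outside the ANOVA, and 9.2 names four domains without saying that each latency, amplitude and sector has its own test.
- That the wording of the objectives makes success on any one outcome sufficient. In 5.5, "Secondary objectives include stabilising and/or improving RGC functionality and optic nerve function assessed with the recording of PERG and VEP", the alternative is between stabilising and improving the same function; it does not offer a choice among outcomes.
- That 49% is a property of this trial. It needs four sectors and complete independence, neither of which is stated.
- That 74% is the rate of false claims of benefit. It includes chance changes in untreated eyes and changes in either direction.

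**Conclusion.** The concern holds in this form: 9.2 has no rule across parameters, its multiple-comparison methods act only within one, and it does not say which acuity measure, contrast or visit decides. For 9–13 parameters, one two-sided 5% test each and correlation 0 to 0.7, the chance of at least one false positive is about 20–49%, or about 10–28% if only apparent benefit counts. It is higher with separate tests in each group. The nine parameters can be counted in 5.6. The four sectors, the correlation range and one test per parameter are assumptions. Even with only one test per domain the figure is 13.0–18.5%, so the conclusion that 5% is exceeded does not depend on the upper count. This should be corrected before the data are unmasked. It does not show that a single pre-specified acuity test would be invalid.

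**What to change.** Add to 9.2:

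1. One primary test: distance acuity in LogMAR, one treated-versus-control contrast, at one stated visit.
2. If that is significant at 5%, test in this order PERG P50-N95 amplitude, VEP P100 implicit time and mean nerve fibre layer thickness. Use the same single contrast and visit, each at 5%, and only while the previous test is significant.
3. Report near acuity, the other latencies and amplitudes, the sectors, the other visit and the within-group changes as estimates with 95% confidence intervals, without significance wording. State how many sectors are reported.

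The list follows the sponsor's own emphasis in 9.1 and 10.1. The order alone would not hold 5%: if a step could be met at either visit, or in either group, the inflation would return inside that step. Contrast and visit must therefore be fixed in the same text.

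The cost is a short rewrite of 9.2 and one real decision, since the present text specifies only within-group analyses. Alpha for acuity stays at 5%, as in 9.1. Whether the before-after differences in 9.1 suit a between-group contrast is a separate question. The main downside is that if acuity fails, the secondary results, including the PERG outcome that set the sample size, are descriptive only.
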